7.2 Measures, Questionnaires and Interviews

A. Main Study

i) *Centre Pathway Review Form (see Appendix 1)*

This is an initial questionnaire which will be completed by the centre director at each site. It is designed to assess the current clinical practice of gastrostomy insertion in patients with MND at each centre. It will record data with regard to the number of gastrostomies performed; the type of gastrostomies offered and the preferred circumstances for each different type; as well as the decision-making criteria influencing the timing of gastrostomy.

ii) *Pre Gastrostomy Patient Evaluation Form (see Appendix 2)*

This evaluation form, which will be completed by the local champion at enrolment, is designed to capture data already being recorded in the neuromuscular clinic as part of routine clinical care. It will record the following data about a recruited patient:

Demographic and functional characteristics: Demographic and functional characteristics of the patients will be recorded including age, gender, date of onset of MND symptoms, date of MND diagnosis, site of onset of MND, severity of bulbar dysfunction, time since first symptom of significant weakness, weight, and height. A functional rating scale for MND/ALS, the Amyotrophic Lateral Sclerosis Functional Rating Scale – Revised (ALSFRS-R) [52] will also be completed (see Appendix 6). These data are available in each patient's medical records.

Measures of respiratory function: Forced vital capacity (FVC); Sniff Nasal Inspiratory Pressure (SNIP); and arterial blood gas or non-invasive measurement of P_{tO_2} - P_{tCO_2} , will be recorded. These parameters of respiratory function are measured routinely in the neuromuscular clinic as part of routine clinical care.

Indices of disease progression: Weight measurement and the ALSFRS-R score will be recorded for each patient. These parameters of disease progression are also measured routinely in the neuromuscular clinic as part of routinely clinical care.

Gastrostomy-related data: The pre-procedure evaluation form will also record data for each patient with regard to gastrostomy indication; type of gastrostomy preferred and preference reasons; potential benefits of gastrostomy; and, patient's influence on the timing of gastrostomy.

iii) Peri-procedure Patient Evaluation Form (see Appendix 3)

This form will be completed at the end of the gastrostomy procedure, either by the local champion or the member of the team performing the gastrostomy insertion. The form is designed to capture the details of the procedure with regard to staffing; gastrostomy equipment; drugs given; patient monitoring and respiratory support; as well as, any complications that occur during the procedure.

iv) 3-month Follow Up Patient Evaluation Form (see Appendix 4)

This form is designed to capture data with regard to gastrostomy complications occurred prior to patient's hospital discharge and those occurred after the hospital discharge up to the 3-month patient evaluation. Weight and ALSFRS-R for each patient will also be recorded. This form will be completed by the local champion after a patient's usual follow up visit which coincides nearest with 3 months post gastrostomy.

v) 12-month Follow Up Patient Evaluation Form (see Appendix 5)

This form is designed to capture data with regard to gastrostomy complications occurred in the period of time between the 3-month patient evaluation and the 12-month patient evaluation. Weight and ALSFRS-R for each patient will also be recorded. This form will be completed by the local champion after a patient's usual follow up visit which coincides nearest with 12 months post gastrostomy.

vi) McGill Quality of Life Questionnaire (MQOL) (see Appendix 7)

This is a well-established questionnaire, designed in the context of palliative care, to identify the health-related quality of life of patients with a terminal illness. It balances physical and non-physical aspects of quality of life, and includes both positive and negative influences on quality of life [53]. This questionnaire will be completed by patients at baseline and at 3 months post gastrostomy.

vii) Modified Caregiver Strain Index (MCSI) (see Appendix 8)

This is a well-established questionnaire, designed to identify the strain levels among informal carers of patients with long-term illness. It will be used in this study to assess the quality of life of the main carer of the patient and the impact that the treatment is having on the carer [54]. It will be completed by carers at baseline and at 3 months post gastrostomy.

viii) Gastrostomy-specific questionnaire (Gastro-Qu) (see Appendix 9)

This is a questionnaire designed to relate the outcomes of gastrostomy insertion to health-related quality of life of patients. It is used to identify the complications and difficulties of gastrostomy as well as its interference with family and social life, from the point of view of patients [55]. It will be completed by patients at 3 months post gastrostomy.

B. Qualitative Interview Study

The qualitative component of PROGAS at Sheffield and Leeds involves the conduct of semi-structured interviews with patients, and their informal carers (10 patients and 10 carers per site), in relation to their experience of gastrostomy insertion and its impact on their quality of life. The advantage of including a qualitative component into PROGAS is that it compensates for any preconceived assumptions inherent in the structured questionnaires, and provides interviewees with the opportunity to talk about what is important to them setting their views in context [56]. This component will assess the outcomes of gastrostomy from the perspective of the patients and carers; delineate their concerns, problems and needs; give an insight of how these needs could be addressed to improve care; and enhance our understanding of the factors that are associated with gastrostomy feeding and impact

on the quality of life. Each patient and each carer will take part in one interview at 3 months following gastrostomy.

i) Interviews with patients

Interviews will be semi-structured and conducted in a location of the participant's choosing after establishing informed consent. The interviews will be recorded. These recordings will be anonymised before being transcribed. All the interviews will be semi structured and therefore the exact details of interview cannot be predicted. Broad themes will be used to offer structure to the interview. These broad themes will be discussed with the Sheffield Motor Disorders Research Advisory Group (SMND-RAG) to enable the public, carers and patients to input in deciding these. Evidence from previous qualitative work on the impact of gastrostomy on quality of life of patients with severe dysphagia due to other underlying conditions, e.g., oral and oropharyngeal cancer, CNS tumours and injuries, multiple sclerosis, dementia, Parkinson's disease, digestive disorders [55, 57-62], will be taken into account when discussing the interview schedule for PROGAS. Once the broad themes have been identified two pilot interviews will be carried out to test the structure. Although yet to be discussed at the SMND-RAG, the broad themes may involve the following issues related to gastrostomy: feeding regimens; quality of life; alleviation of problems present prior to gastrostomy; support from healthcare professionals; difficulties encountered; feed administration/delivery; impact of feeding on daily, social and family life; impact on relationships. Each theme will be introduced with an open ended question, e.g., "Do you experience any difficulties that arise directly from gastrostomy feeding and how do they impact on your daily life?" Further follow on questions depending on the initial discussion would explore both issues important to the patient regarding this theme and also issues identified by the SMND-RAG.

We will be sensitive to the preferences of the participants about whether patients and carers will be interviewed together (conjoint) or will be interviewed separately or a combination of both. Interviewers will be sensitive to the emotional and physical state of the participants and if they become upset or tired, the interview will stop. After every interview, individual or conjoint debriefing sessions will take place to talk about the situations or feelings that may have triggered their emotions. In the final phase of the illness, patients may be too tired and unwell to participate. We will be sensitive to the patient's wishes with regard to participation and will re-establish consent. If the patient would like to participate, but is physically unable, in agreement with all parties, we will invite the carer to be a proxy and review the responses with the patient so they remain involved [63].

ii) Interviews with the informal carers of patients

Similarly, interviews with the informal carers of MND patients with a gastrostomy will be conducted in a location of the participant's choosing after establishing informed consent. The interviews will be recorded and these recordings will be anonymised before being transcribed. The interviews will follow a similar semi-structured design and the broad themes will be decided as described above. We will stop interviews if carers become distressed and facilitate appropriate counselling.

7.3 Participant Involvement in PROGAS

Patients will undergo routine clinical assessments, related to the gastrostomy procedure, before and during the actual operation. Following gastrostomy, patients will undergo routine assessments at their usual visits to the neuromuscular clinic at each participating site. PROGAS-only related assessments include completion of the MQOL and Gastro-Qu, and participation in a qualitative interview (for patients at Sheffield and Leeds sites only). The following table (Table 1) shows a detailed grid of all the patient assessments undertaken during PROGAS.

Carers involvement in PROGAS requires no other assessments than completion of the MCSI (at baseline and 3 months post gastrostomy) and participation in a qualitative interview (for carers at Sheffield and Leeds sites only).

PROGAS	Sheffield and Leeds MND Centres				Other participating MND Centres			
	Pre Gastrostomy	Peri Procedure	3 months Follow up	12 months Follow up	Pre Gastrostomy	Peri Procedure	3 months Follow up	12 months Follow up
Weight	✓	-	✓	✓	✓	-	✓	✓
Height	✓	-	-	-	✓	-	-	-
FVC%	✓	-	-	-	✓	-	-	-
SNIP	✓	-	-	-	✓	-	-	-
pO ₂	✓	-	-	-	✓	-	-	-
pCO ₂	✓	-	-	-	✓	-	-	-
O ₂ Sats	✓	-	-	-	✓	-	-	-
Heart rate	-	✓	-	-	-	✓	-	-
Respiratory rate	-	✓	-	-	-	✓	-	-
Blood pressure	-	✓	-	-	-	✓	-	-
CO ₂	-	✓	-	-	-	✓	-	-
ALSFRS-R	✓	-	✓	✓	✓	-	✓	✓
MQOL	✓	-	✓	-	✓	-	✓	-
Gastro-Qu	-	-	✓	-	-	-	✓	-
Interview	-	-	✓	-	-	-	-	-

Table 1: Grid of patient assessments undertaken during PROGAS

7.4 Participants and Recruitment

Inclusion & Exclusion Criteria

Patients, and their carers, will be recruited locally at the participating centres. Patients with MND will be eligible when a decision has been made to refer the patient for a gastrostomy, regardless of indication.

Patient Inclusion Criteria:

- i) A diagnosis of definite, probable, laboratory supported or possible MND, as defined by the revised El-Escorial criteria
- ii) A decision has been taken to refer the patient for a gastrostomy

Patient Exclusion Criteria:

- i) Contradiction to gastrostomy
- ii) Patient declines gastrostomy

Carer Inclusion Criteria:

- i) Being the main carer of an MND patient who has been referred for a gastrostomy placement.

Carer Exclusion Criteria:

- i) Patient declines to participate in an interview (only for the qualitative component of PROGAS)

Participant Recruitment

Patients and their carers will be recruited at each of the participating sites. A typical site (Sheffield Care and Research Centre for Motor Neurone Disorders), serving a population of approximately 2.2million undertakes approximately 16 gastrostomies per year for patients with MND. With the inclusion of 18 sites, and anticipating an 80% participant response rate, we estimate that we will recruit at least 504 patients over a 21-month recruitment period.

Patients and carers will be informed of the study after a decision to refer for a gastrostomy has been made by a member of the research team. Patients and carers who are not interested will not be contacted again for this study. A patient information sheet, explaining the details of the study, will be given to interested patients meeting all the inclusion criteria and none of the exclusion criteria and a carer information sheet will be given to interested carers. They will be asked to contact the local researcher if they would like to participate in the study. One follow up call will be made by a member of the research team, to initially interested patients and carers who do not contact the local researcher, approximately two weeks following the invitation. Patients and carers who respond negatively to the follow up call will not be contacted again for this study. Patients and carers who contact the local researcher and those who respond positively to the follow up call will be asked to provide their consent for participation in the study.

Once consented and successfully recruited into the study the participants will be further informed verbally about the next stages of PROGAS by the local researcher and undergo the gastrostomy procedure as scheduled. Data will be collected, by a member of the research team, before and following the gastrostomy procedure with the completion of the pre-procedure and the peri-procedure gastrostomy patient evaluation forms, respectively. Following hospital discharge, the participants will continue their standard visits (approximately every 2-3 months) to the neuromuscular clinic as part of routine clinical care.

For this study data will also be collected, by a member of the research team, 3 months and 1 year following gastrostomy.

During their participation into PROGAS, patients will be asked to complete a health-related quality of life questionnaire (MQOL) twice (at baseline and approximately at 3 months following gastrostomy), and a gastrostomy-specific questionnaire once (approximately at 3 months following gastrostomy). Participating carers will be asked to complete a quality of life questionnaire (MCSI) twice (at baseline and approximately 3 months following gastrostomy). Both patients and carers will be given freepost/pre-paid envelopes to return the questionnaires to the study's central co-ordinator.

The recruitment process of patients and carers for the qualitative component of PROGAS at Sheffield and Leeds MND Care and Research Centres will be similar to the process described above. Once consented and recruited, participants will be contacted by the local researcher by telephone (approximately 3 months following the gastrostomy procedure) to arrange with each one a date and time for a face-to-face interview at a place of each participant's choice. For this part of PROGAS, we will aim to recruit 10 patients and 10 carers. Quantitative data will be collected as described for the other sites. A detailed visual representation of the recruitment process is shown in the following chart (Chart 1).

[figure not shown]

Chart 1: Participant recruitment flow chart

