7.1 Plan of Investigation

A. Centre Pathway Review

We have 15 MND centres committed to participating in PROGAS. A provisional survey of the centres has identified that 360 gastrostomies are performed for MND patients in the UK per year. The first component of PROGAS will be to perform a detailed survey of current practice regarding gastrostomy pathways at each centre. A questionnaire will be completed by the director of each centre capturing data regarding indication for gastrostomy, timing, and type of gastrostomy. This survey will highlight current practice, good practice points and will enable refinement of the data analysis plan of the main phase of the study. The centre director will also identify a “local champion” who will assist in recruiting patients and liaise with the central study co-ordinator who will be based in Sheffield.

B. Prospective evaluation of Gastrostomy

Following ethical and research governance approvals, participants will be recruited into PROGAS from all participating sites over a period of 21 months. All centres will be encouraged to maintain their usual practice and protocols for gastrostomy provision.

i) Patient enrolment

The study will be discussed with patients and carers, when a gastrostomy is being considered by the clinical team as part of their normal standard care. Patients and carers will be asked to consent to the study at the time of referral for gastrostomy. We will aim to recruit 504 patients and carers over 21 months. This figure is based on 80% (i.e., the anticipated patient response rate) of the 630 eligible patients seen according to the provisional survey of centres undertaken.

ii) Pre Gastrostomy Patient Evaluation

Once patients are successfully recruited and consented into PROGAS, the local investigator will complete a Pre Gastrostomy Patient evaluation form. This form is designed to capture routine data already being recorded in clinics, including demographic and functional characteristics, nutritional and respiratory status and gastrostomy-related data.

iii) Peri-Procedure Evaluation

Patients will then undergo the gastrostomy procedure. At the end of the procedure, either the local investigator or a member of the team performing the gastrostomy insertion will complete a Peri-procedure evaluation form. This form will capture the details of the procedure as well as any complications that occur during the procedure.

iv) Follow Up Patient Evaluation

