7.6 Statistical Power Analysis

There are few studies in the MND literature comparing survival time or one month post procedure mortality of patients with MND following different methods of gastrostomy. Three recent studies [24, 34, 47] reported that there was no significant difference in survival between PEG patients and RIG patients. These studies were retrospective, contained small numbers and were not adequately powered to detect potentially important clinical differences. One small prospective study [30] reported that there was a significant difference ($p = 0.004$) between survival in PEG patients and survival in RIG patients but this was in the subgroup of patients with respiratory failure. The median survival after gastrostomy was 140% higher in the RIG group compared to PEG group. Given the lack of comparative studies we have reviewed the literature for mortality data. For MND patients undergoing PEG the 30 day mortality rates range from 4% to 25% [19, 26, 30-32, 47-51]. For MND patients undergoing RIG procedures the 30 day mortality rate ranges from 4% to 9% [30, 35, 47].

Based on the review of the literature we hypothesise that a difference in one month mortality between PEG and PIG/RIG of between 0 % and 21% may exist. We aim to power PROGAS to detect a conservative, but clinically important, 30 day mortality rate difference of 8%. Power analysis calculations indicated that a minimum sample of 442 patients would be required to attain sufficient statistical power. For PROGAS, anticipating an 80% participant response rate over a 21-month recruitment period, we estimate that we will recruit 504 patients. This sample size will provide statistical power of 80% at a 5% level of statistical significance to detect a difference of 8% in mortality at one month, using a continuity corrected Chi-square (χ^2) test.

We aim to identify the most appropriate method of gastrostomy in terms of safety and patient experience. The study is designed to be easily carried out in a routine clinical setting and to assess in a pragmatic way current practice throughout the UK. It is clear that multiple variables at different sites may impact on the outcomes. However the key variables including MND disease course, nutritional and respiratory status, are being recorded and we will

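### The recruitment inputs in section 7.4 yield about 403 patients, not 504, and conflict with the survey basis in section 7.1; the two bases fall on opposite sides of the protocol's minimum of 442

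*Protocol*

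**What the plan says.** Section 7.4 describes the Sheffield centre as a typical site that "undertakes approximately 16 gastrostomies per year for patients with MND". The next sentence reads "With the inclusion of 18 sites, and anticipating an 80% participant response rate, we estimate that we will recruit at least 504 patients", and the estimate is made "over a 21-month recruitment period".

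Section 7.1 gives another route to the same number. It says "We have 15 MND centres committed to participating in PROGAS" and then "A provisional survey of the centres has identified that 360 gastrostomies are performed for MND patients in the UK per year". Of the 504 target it says "This figure is based on 80% (i.e., the anticipated patient response rate) of the 630 eligible patients seen according to the provisional survey of centres".

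Section 7.6 states that "a minimum sample of 442 patients would be required to attain sufficient statistical power". It repeats 504 as the expected recruitment after 80% response, and attaches 80% power at the 5% level to it, for an 8-point difference in 30-day mortality with a continuity-corrected chi-square test. Section 8.1 provides centre codes from 01 to 18.

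**The concern.** A reader who multiplies the figures placed together in section 7.4 gets exactly 504 before any allowance for non-response. The sentence presents 504 as the number left after 80% response. On its own inputs the statement is therefore too high by a factor of 1/0.8.

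Section 7.1 arrives at 504 correctly, but from an annual volume that does not match 16 procedures at 18 sites. The site count also differs (15 against 18), and the 360 procedures are described as those done in the UK rather than clearly those at the participating sites.

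What is at stake is whether the primary comparison reaches its own minimum size. One base clears 442 and the other misses it.

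**Working it through.** **Inputs.** Section 7.4: about 16 gastrostomies per year at a typical site, 18 sites, 80% response, 21 months (21/12 = 1.75 years). Section 7.1: 360 gastrostomies per year, 630 eligible patients, 80% response, 15 committed centres. Section 7.6: minimum 442, difference 8 points, 80% power, 5% level, continuity-corrected chi-square. The arm rates and the sidedness of the test are not stated.

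**Formula.** Recruits = procedures per year × 1.75 × 0.80.

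**Step 1: reproduce the plan's figure from section 7.1.** 360 × 1.75 = 630, and 630 × 0.80 = 504. This agrees exactly with the stated 630 and 504.

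**Step 2: apply the inputs of section 7.4.** 16 × 18 = 288 per year. 288 × 1.75 = 504 eligible. 504 × 0.80 = 403.2 recruited.

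**Step 3: compare.**

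| Base | Procedures per year | Eligible | Recruited | Against 442 |
|---|---|---|---|---|
| Section 7.1 (survey) | 360 | 630 | 504 | +62 |
| Section 7.4 (16 × 18) | 288 | 504 | 403 | −39 |

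403 is 20% below 504 (101/504) and 9% below 442 (39/442).

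**Step 4: what mean volume per site would be needed?**
- For 504 recruits from 18 sites: 504 / (0.80 × 1.75 × 18) = 20.0 per year.
- For 442 recruits from 18 sites: 442 / (0.80 × 1.75 × 18) = 17.5 per year.
- If the 360 all came from the 15 committed centres: 360 / 15 = 24 per year.

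**Step 5: power at 403.** Assumptions: two-sided 5%, equal groups of n = N/2, and arm rates p1 and p2 that differ by 0.08. With p̄ = (p1 + p2)/2,

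power = Φ{[0.08 − 1/n − 1.96·√(2p̄(1 − p̄)/n)] / √([p1(1 − p1) + p2(1 − p2)]/n)}.

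For N = 403, 12% v 4%: n = 201.5, and the two standard errors are 0.0270 (null) and 0.0267 (alternative). The standardised value is 0.825, so power is 79.5%.

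| Assumed rates | N = 403 | N = 442 | N = 504 |
|---|---|---|---|
| 12% v 4% | 80% | 84% | 88% |
| 12.8% v 4.8% | 76% | 80% | 86% |
| 14.4% v 6.4% | 70% | 74% | 80% |

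The second row is the pair at which 442 gives 80% power. The third is the pair at which 504 does. The first takes 4%, the low end of the RIG range quoted in section 7.6.

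**The case against.** The strongest reply is that section 7.1 states where 504 comes from. It is 80% of 630 surveyed patients, it reproduces exactly, the response rate is applied once, and the result exceeds 442. Section 7.4 never writes out 16 × 18 × 1.75. The 16 belongs to one named centre, and a typical volume need not be the mean: a few large centres could lift the mean to 20 while 16 remains typical. This stands. A reader might infer that expected recruitment is really 403 and that the 80% was forgotten. The document does not support that, because it gives a coherent separate derivation and no per-site volumes.

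A reader might also go further and combine 15 centres with 16 procedures a year, which gives 15 × 16 × 1.75 × 0.80 = 336. That pairs the lower count with the lower volume. Section 7.4 and the codes in section 8.1 both point to 18 operating sites, so 336 should not be put forward as a restated figure.

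The loss of power is also conditional. The arm rates are assumptions, and at 12% v 4% a sample of 403 still gives almost exactly 80%.

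The reply does not rescue section 7.4 as written. Its figures do not yield the number it states, and 288 a year is not 360 a year. If the mean is 20, the text should say so. Nor does the survey base settle the matter, since it is described as UK procedures and stands beside 15 centres.

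**Conclusion.** The point holds as an unreconciled contradiction between two recruitment bases, not as a demonstrated expectation of 403. On the figures beside it, section 7.4's statement of at least 504 recruits is unsupported: they give about 403, which is 39 short of the protocol's own minimum. The survey base in section 7.1 gives 504, which is 62 above it.

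The figure of 403 rests on one assumption, that 16 per year is the mean over 18 sites. The figure of 504 rests on another, that all 360 surveyed procedures occur at participating sites. Neither can be confirmed from the protocol. That 403 is below 442 needs no mortality assumption. The size of any power loss does: about 70% to 80% at 403, for assumed rates from 14.4% v 6.4% to 12% v 4%, equal groups and a two-sided test.

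It deserves correction because the recruitment figure is what section 7.6 relies on for adequate power.

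**What to change.** Reconcile sections 7.1 and 7.4 from the per-centre counts in the provisional survey:

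1. State one number of participating sites in both sections.
2. Give the surveyed mean per site, or the total at the participating sites, and say whether the 360 refers to those sites or to the whole UK.
3. Correct the inputs in section 7.4 so that, multiplied out and reduced by the 80% response rate, they give the stated recruitment. If 504 rests on 360 a year at 18 sites, the figure to show is a mean of 20; the 16 can stay as a description of one centre.
4. If the counts do not support 504 at the participating sites, restate expected recruitment and its power in section 7.6, and name the arm rates used.

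The cost is wording and counts that the survey should already hold. If step 4 applies, the protocol would also carry a less favourable recruitment and power figure.
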